7.2 Statistical Analyses of the Secondary Objectives

- (a) To identify potential blood-based radiation response biomarkers, we will estimate mean (with 95% CI) and median change in circulating free DNA from pre- to post-RT, by level of biomarker.
- (b) Quality of life (FACT-B) and patient satisfaction will be measured at baseline and at 6, 12, 24, and 36 months. For each scale, the mean and its 95% CI's will be estimated at each time point; boxplots will be used to estimate the distribution of these scales at each time point.
- (c) Time to local or regional failure will be defined as the time from start of treatment to date of local or regional failure, whichever comes first; distant failures will be ignored; deaths will be censored. Time to distant failure will be defined as the time from start of treatment to date of distant failure; local and regional failures will be ignored; deaths will be censored. The Kaplan Meier method will be used to estimate both of these distributions.

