3 PROTOCOL SYNOPSIS

3.1 Purpose

This protocol seeks to utilize a novel method of tumor bed boost delivery and to better understand breast cancer radiation response through the analysis of pre-and post-radiation samples.

Primary Objective:

1. Determine physician and patient-reported rates of good/excellent cosmesis at baseline and 6 months, 1, 2, and 3 years post-treatment as measured by the NRG cosmesis scale.

Secondary Objective:

1. Evaluate changes in circulating free DNA pre and post-radiation in order to identify potential blood based radiation response biomarkers.
2. Assess patient-reported Quality of Life (FACT-B) and patient satisfaction at the same time points as above (primary objective).
3. Assess local control in the treated breast relative to historical controls.
4. To review treatment plans, evaluate delivery techniques, and assess positioning verification images.

Hypotheses

We hypothesize that the boost can be delivered preoperatively to the intact breast tumor with acceptable cosmetic outcomes. Furthermore, we anticipate that pre- and post-radiation blood samples will provide an avenue for understanding breast cancer radiation response.

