6 PATIENT ASSESSMENTS

Assessment	Pre-Tx.	Follow-up
Consent	X	
History/Physical	X	X ^a
Complete Blood Count (no differential)/CMP	X	
Breast imaging (mammogram minimum)	X ^g	X ^a
Core Biopsy/Fiducial Markers	X ^b	
Planning MRI	X	
Surgical Excision		X ^c
Acute Toxicity Evaluation		X ^d
Cosmetic Evaluation Form/Digital Photographs/QOL	X ^e	X ^e
Clinical Outcomes		X ^a
Serum Collection	X ^f	X ^f

- Physical exam by member of oncology team recommended every 4-6 months for 2 years, every 6 months through year 5 and annually years 5-10. Bilateral mammogram recommended at least annually.
- Verify placement of a biopsy clip at diagnostic procedure.
- Within 2-4 days following radiation (up to 7 allowed if needed – see below).
- Appointment by a radiation oncology physician/mid-level provider 1-2 months post-radiation.
- At baseline (prior to treatment), six months and one year after treatment and then annually for 2 additional years. To be filled out by both patient and physician/mid-level provider. Digital photographs at the same time points and at investigator’s discretion.
- 2 lavender tubes drawn prior to radiation therapy and post radiation therapy (before surgery)
- Mammogram will not be repeated if one has been obtained within 6 months of signed study consent. Mammography does not need to be repeated unless clinically indicated.

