6.1 Pretreatment Evaluations/Management

Prior to treatment each patient will be required to have a complete history and physical including signed informed consent, basic clinical laboratory studies, staging and a biopsy demonstrating ductal carcinoma in situ or invasive breast carcinoma.

Assessment of the tumor by physical exam and mammogram (further imaging at radiologist/physician discretion) should include tumor measurements. Each patient will complete a baseline cosmetic evaluation as will her physician/mid-level provider. QOL measures will also be assessed. Prior to study treatment, placement of a biopsy clip at the time of diagnostic biopsy will be verified as this will serve as a fiducial marker (described in section 8.2) to assist in radiotherapy localization. MRI and CT of the affected breast will then be completed in Radiation Oncology for radiation treatment planning.

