6.3 End of Treatment/Follow-up Period

Lumpectomy will be completed 2-4 days (though up to 7 days will be allowed for logistical constraints without considering this a protocol deviation) following RT delivery. Tissue will be processed as described below in section 8.1. A surgical margin will be considered negative if there is no ink on tumor. The patient will be assessed by a Radiation Oncology physician/mid-level provider within 2 months after preoperative treatment, to evaluate for treatment toxicity. Subjects will then go on to complete systemic therapy as indicated or proceed to conventional radiation.

Subjects will be seen weekly during conventional treatment as is standard procedure in our department. Follow-up after conventional radiation will follow national guidelines and includes a history and physical every 4-6 months for the 1st 2 years, every 6 months to a year through year 5 and annually through year 10. Mammograms will be obtained at least annually. Other laboratory or radiographic studies will be obtained as directed by patient symptoms or physical exam. Quality of life and cosmetic assessments, physician/mid-level provider and patient, will be performed at 6 month, 1 year, and then annually through 3 years of follow-up as will digital photographs. Locoregional recurrence will be monitored on protocol at each follow-up visit.

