APPENDIX III: Patient Self-Assessment

1. Please assess the cosmetic outcome of your treatment. (Circle the number next to the word that best describes the appearance of the breast.)

- 1 Excellent - when compared to the untreated breast, there is minimal or no difference in the size, shape or texture of the treated breast. There may be mild thickening or scar tissue within the breast or skin, but not enough to change the appearance.
- 2 Good - there is mild asymmetry in the size or shape of the treated breast as compared to the normal breast. The thickening or scar tissue within the breast causes only a mild change in the shape.
- 3 Fair - there is obvious difference in the size and shape of the treated breast. This change involves 1/4 or less of the breast.
- 4 Poor - marked change in the appearance of the treated breast involving more than ¼ of the breast tissue.

2. How satisfied with your treatment are you?

Extremely satisfied Very Satisfied Satisfied Unsatisfied

3. Would you choose this treatment again?

Yes No

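### Section 7.2(b) would be improved by adding FACT-B change from the baseline already collected, and by reporting satisfaction as category proportions at follow-up visits

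*Combined protocol and SAP*

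**What the plan says.** Secondary Objective 2 in section 3.1 reads: "Assess patient-reported Quality of Life (FACT-B) and patient satisfaction at the same time points as above (primary objective". Section 7.2(b) sets the schedule: "Quality of life (FACT-B) and patient satisfaction will be measured at baseline and at 6, 12, 24, and 36 months". The whole planned analysis is then: "For each scale, the mean and its 95% CI's will be estimated at each time point; boxplots will be used to estimate the distribution", visit by visit.

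Baseline quality of life is collected. The assessment table in section 6 has a row "Cosmetic Evaluation Form/Digital Photographs/QOL" marked both before treatment and at follow-up, and section 6.1 says of the pre-treatment work-up that "QOL measures will also be assessed".

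Satisfaction is measured in Appendix III. One item asks "How satisfied with your treatment are you", with the answers "Extremely satisfied Very Satisfied Satisfied Unsatisfied" and no printed numeric codes. A further Yes/No item asks whether the woman would choose the same treatment again. The plan does not say which of the two makes up patient satisfaction.

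No section plans a change from baseline in FACT-B, a paired or repeated-measures analysis, or counts by satisfaction category. Section 7.2(a) does plan a mean pre-to-post change with a 95% CI, but only for circulating free DNA.

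**The concern.** With one arm, each woman's own pre-treatment FACT-B score is the only comparator inside the study. Reporting each visit separately leaves that comparison to the reader, who cannot make it properly. With complete data the difference between two visit means equals the mean change, but its confidence interval cannot be recovered. With incomplete follow-up, the difference also mixes real change with who came back.

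For satisfaction, the plainest result is how many women were Unsatisfied, the only negative answer offered. A mean needs codes that the plan does not give, and neither a mean nor a boxplot of four values reports that share.

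Finally, a question about satisfaction with treatment is scheduled before treatment has been given, and 7.2(b) would summarise the answers.

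**Working it through.** Section 7.2(b) states no precision or power, so there is no plan figure to reproduce.

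**Inputs.** N = 40 in a single arm (sections 3.4 and 7.1); four ordered answers (Appendix III). The documents give no FACT-B SD, no baseline-to-follow-up correlation r and no dropout rate. The following are therefore assumptions: equal SDs at both visits; r = 0.3, 0.5 and 0.7; 40 or 30 pairs; satisfaction coded 1 (Extremely satisfied) to 4 (Unsatisfied).

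**1. Visit intervals do not give an interval for change.**

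- Half-width for a visit mean, n = 40: t(39) / √40 = 2.023 / 6.325 = 0.32 SD, whatever r is.
- Half-width for mean paired change: t(n−1) × √(2(1−r)/n), in SD units.

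| Pairs | r = 0.3 | r = 0.5 | r = 0.7 |
|---|---|---|---|
| 40 | 2.023 × √(1.4/40) = 0.38 | 2.023 × √(1.0/40) = 0.32 | 2.023 × √(0.6/40) = 0.25 |
| 30 | 2.045 × √(1.4/30) = 0.44 | 2.045 × √(1.0/30) = 0.37 | 2.045 × √(0.6/30) = 0.29 |

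The planned visit intervals are the same in every column, while the interval for change is not. They do not carry the within-woman correlation.

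**2. Dropout.** Suppose 10 of 40 women do not return, that they scored d lower at baseline than the 30 who do, and that no returning woman changes. With μ the baseline mean of the returners:

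- Baseline mean of all 40: μ − (10/40)d.
- Follow-up mean of the 30: μ.
- Apparent difference: 0.25d. This is 0.125 SD for d = 0.5 SD and 0.25 SD for d = 1 SD.

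The paired change in the same 30 women is 0.

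**3. Satisfaction.** Take two possible results for 40 women, in the order Extremely / Very / Satisfied / Unsatisfied:

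| | 16/5/18/1 | 12/17/6/5 |
|---|---|---|
| Sum | 16+10+54+4 = 84 | 12+34+18+20 = 84 |
| Sum of squares | 16+20+162+16 = 214 | 12+68+54+80 = 214 |
| Mean | 2.10 | 2.10 |
| SD, √((214 − 40 × 2.10²)/39) | 0.982 | 0.982 |
| 95% CI of mean | 1.79–2.41 | 1.79–2.41 |
| Quartiles | 1, 2, 3 | 1, 2, 3 |
| Whiskers; outliers | 1–4; none | 1–4; none |
| Unsatisfied | 1/40 = 2.5% | 5/40 = 12.5% |
| Exact (Clopper-Pearson) 95% CI | 0.1–13.2% | 4.2–26.8% |

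Everything 7.2(b) asks for is identical, yet the number unsatisfied differs by four women (10 percentage points).

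**4. Baseline satisfaction.** Sections 3.1 and 7.2(b) both include baseline among the visits for satisfaction. The footnote to the assessment table puts baseline before treatment. The item asks about the woman's treatment, so there is no clear object for an answer at that visit.

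**The case against.** The strongest reply is that the plan does what its objective asks. Objective 2 is only to assess these measures at the listed visits, and the hypotheses in section 3.1 concern cosmesis and blood samples, not change in quality of life. That stands: a reader might infer that 7.2(b) contradicts the objective, and it does not. A small descriptive study may report visit summaries, and paired analysis remains possible later because the data exist. What remains is that the choice of visits and women would then be made after the data are seen, although 7.2(a) prespecifies a change for another measure.

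Second, change from baseline would not isolate the boost. After surgery, "Subjects will then go on to complete systemic therapy as indicated or proceed to conventional radiation", so the change reflects the whole course. This is right and limits the value of the added number. Paired change also describes only women who returned, so it removes the artefact in step 2 without saying anything about those lost.

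Third, a reader might set the paired half-widths against the roughly 0.45 SD obtained by treating two visits of 40 women as independent (t(78) × √(2/40)) and call the difference a loss of precision in the plan. The documents do not support this: 7.2(b) computes no difference between visits and assumes no independence.

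Fourth, a reader might infer that the assessment table omits satisfaction because its row names only cosmesis, photographs and QOL. The footnote to that row has the form completed by the patient as well as the clinician. The patient's form is most naturally Appendix III, which contains the satisfaction items. The table therefore agrees with sections 3.1 and 7.2(b).

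Fifth, the example in step 3 is constructed, and one of its splits has two peaks. It shows that the planned output need not determine the share Unsatisfied, not that it usually fails to. If all 40 women answered Very Satisfied, for instance, a mean of 2 with SD 0 would settle the matter. Likewise, if the Yes/No item is part of the endpoint and is coded 0/1, its mean already is a proportion.

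**Conclusion.** The point holds as a minor improvement to a descriptive secondary analysis. It is an omission, not an error or a contradiction. The plan provides no interval for FACT-B change, no protection against comparing different women across visits, and no report of the share Unsatisfied; it also schedules a baseline satisfaction summary that is hard to interpret.

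With 40 pairs the added FACT-B change would have a 95% half-width of about 0.25 to 0.38 SD for r from 0.7 down to 0.3. The dropout artefact avoided would be 0.125 to 0.25 SD in the scenarios shown. These sizes rest on assumed SDs, correlations and losses and are not evidence about this trial. The absence of the analyses, and the fact that a mean and boxplot need not fix the Unsatisfied count, do not depend on them; the worked example assumes codes 1–4 and complete answers. The primary cosmesis rule and N = 40 are unaffected.

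**What to change.** Amend section 7.2(b) as follows.

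- **FACT-B:** keep the visit means and boxplots. Add mean change from baseline with 95% CI and number of pairs at each of the four follow-up visits, from paired data or from a repeated-measures model using all available data. State that the change reflects the whole course of treatment and not the boost alone, and that a paired analysis describes only women who returned.
- **Satisfaction:** state which Appendix III items make up the endpoint. At follow-up visits, report number and percent in each of the four categories, the proportion Unsatisfied with exact 95% CI, and the proportion answering Yes to the choose-again item with exact 95% CI.
- **Baseline satisfaction:** state that any answer collected before treatment will not be analysed.

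The cost is a few sentences of SAP text and a little analysis work. No new data, visits or patients are needed.

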3.4 Selection of Subjects and Sample Size

Women judged by clinical stage as someone to whom a tumor bed boost would be offered during conventional radiation therapy will be eligible. As a general guideline, this typically includes women with invasive cancer that are eligible for and electing breast-conserving therapy under the age of 60. Selected women greater than 60 may also be offered a boost at the discretion of the treating investigator. For example, known nodal involvement may prompt a boost in this scenario. Women with in situ cancers <50 are also typically offered a boost though again, certain women greater than 60 may also be included at the discretion of the treating physician.

The final sample size is 40 subjects. Given the broad eligibility criteria and the more than 400 new subjects with invasive breast cancer seen in Radiation Oncology at Duke each year, accrual is anticipated to be complete in 3 years once the first patient is enrolled.

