7.1 Statistical Analysis of Cosmetic Outcome

This trial will accrue a total of 40 patients over 3 years. The rate of *physician-reported* good/excellent cosmetic outcome will be estimated at baseline and at the following four follow-up time points: 6, 12, 24, and 36 months. A true rate of good/excellent cosmetic outcome rate of ≥ 0.80 would be considered acceptable, while a true rate of ≤ 0.60 would be unacceptable. The cosmetic outcome rate at 6-months will be monitored with the following rules.

Sample size	Review patient data if and when the number of patients with fair/poor cosmetic outcome at 6 months is:
20	≥ 8
40	≥ 12

Specifically, if and when 8 or more of the first 20 patients (40%) have a fair/poor outcome, or if and when 12 or more of the 40 patients (30%) have a fair/poor outcome, the data will be reviewed and a decision will be made whether to close the trial. In other words, least 29 of the 40 patients (0.725) must have a good/excellent cosmetic outcome in order to consider the cosmetic outcome rate acceptable. If the true cosmetic rate is 0.60 and 0.80, then the probability that the rules above will call for a review is 0.93 and 0.10, respectively. Assuming an observed good/excellent cosmesis rate of 0.75, a sample size of 40 will provide a 95% CI's of 0.62 – 0.88.

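### Secondary objective 3 concerns local control in the treated breast, but Section 7.2(c) plans only local-or-regional and distant failure curves, so no in-breast estimate is specified

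*Combined protocol and SAP*

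**What the plan says.** Section 3.1 lists as the third secondary objective: "Assess local control in the treated breast relative to historical controls". The target is one site, the treated breast, and the comparator is external.

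Section 7.2(c) is the only analysis that corresponds to it. It states: "Time to local or regional failure will be defined as the time from start of treatment to date of local or regional failure", taking the earlier of the two. For this endpoint, "distant failures will be ignored; deaths will be censored". A second endpoint, time to distant failure, is defined in parallel, and then: "The Kaplan Meier method will be used to estimate both of these distributions". Those two curves are the whole plan for disease control.

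Three other places bear on the point:

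- Section 6.3, on data collection: "Locoregional recurrence will be monitored on protocol at each follow-up visit". It gives no separate rule for recurrence in the breast.
- Section 3.4, on selected women over 60 who may be offered a boost: "known nodal involvement may prompt a boost in this scenario". Women with involved nodes can therefore enter.
- Section 5.2, under post-operative radiation, has recurrence recorded separately for women found at surgery to need mastectomy, and cautions against comparing their secondary endpoints with those of women whose breast is conserved.

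No section names a historical series, a historical rate, a follow-up year or a method of comparison for local control.

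**The concern.** The objective and the analysis measure different things. Under 7.2(c) a nodal recurrence is an event, and a woman whose first failure is regional leaves the risk set at that date. A later recurrence in her breast is then not counted as such. The objective asks only about the breast, which is also where the study treatment is aimed: Section 5.2 directs the single fraction at the tumor plus a margin, and Section 3.3 justifies the boost by its local control benefit. Nodal treatment belongs to standard post-operative care.

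At stake is whether the trial can report the quantity it set out to report. Without a pre-specified in-breast endpoint, either the composite is presented as local control, or a local-only curve and a benchmark are chosen after the data are seen. The second would weaken a historical comparison that is already limited by the sample size.

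**Working it through.** Section 7.2(c) gives no rate, landmark or power for local control, so there is no stated figure to reproduce. The check has two parts: setting the texts side by side, and finding the direction and size of the gap under labelled assumptions.

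**1. Objective against analysis.**

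| Element | Objective 3 (Section 3.1) | Section 7.2(c) |
|---|---|---|
| Site | Treated breast | Breast or regional nodes, whichever fails first; separately, distant |
| Comparator | Historical controls | None named |
| Time point | None | None |
| Estimator | None | Kaplan-Meier, deaths censored |

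Neither planned curve estimates the first row of the objective.

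**2. Direction.** Every woman with a local failure by time t has a composite failure by time t, and women with a regional failure only are added. The composite risk is therefore at least the local risk. The same ordering holds for the estimates when everyone is followed to t. With uneven censoring, a Kaplan-Meier estimate could depart from it only through a woman who fails regionally and later locally.

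**3. Size.** The inputs are assumptions, not figures from the documents: local risk L = 5% and regional risk R = 0% to 5% at a common landmark, independent of each other. The formula is composite = 1 − (1 − L)(1 − R).

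- R = 0%: 1 − 0.95 × 1.00 = 5.0%
- R = 1%: 1 − 0.95 × 0.99 = 0.0595, or 6.0%
- R = 2%: 1 − 0.95 × 0.98 = 0.0690, or 6.9%
- R = 5%: 1 − 0.95 × 0.95 = 0.0975, or 9.8%

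The excess runs from 0 to 4.75 points. With L = 2% the composite runs from 2.0% to 6.9%, and with L = 10% from 10.0% to 14.5%. If local and regional failures cluster in the same women, the excess is smaller.

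**4. Chance that the endpoints differ at all.** The sample size is from Section 7.1: "This trial will accrue a total of 40 patients over 3 years". The chance of at least one regional failure among 40 is 1 − (1 − R)^40, which is 33%, 55% and 87% for R = 1%, 2% and 5%.

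**5. Precision.** One event in 40 is 1/40 = 2.5 points. Exact 95% limits, ignoring censoring:

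- 0/40: upper limit 1 − 0.025^(1/40) = 8.8%
- 2/40 (5.0%): 0.6% to 16.9%

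If mastectomy subjects are set aside, the denominator falls below 40 and these limits widen.

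**6. Censoring deaths.** Assume constant hazards, with a Kaplan-Meier local failure estimate of 5.0% and a death risk d calculated in the same way. Then a = −ln(0.95), b = −ln(1 − d), and cumulative incidence = [a/(a + b)] × [1 − 0.95(1 − d)].

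- d = 5%: 0.500 × 0.0975 = 4.88%
- d = 10%: 0.327 × 0.145 = 4.75%
- d = 20%: 0.187 × 0.240 = 4.49%

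This is a small effect, of at most about half a point.

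**The case against.** The strongest reply is that the composite may be what the sponsor meant. Section 6.3 monitors locoregional recurrence, Section 3.3 cites guidelines that tie the boost to higher locoregional risk, and Section 5.2 allows regional nodal treatment after surgery. On that reading, Section 3.1 is loosely worded and rewording the objective would also remove the mismatch. This stands as a possibility. But the objective names the treated breast explicitly, and the boost acts there, so adding the missing curve is the change that lets the trial answer the question as written.

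A second reply is that a local-only curve can be drawn later. That is true if site of failure is recorded and follow-up for breast recurrence continues after a regional failure. The separate local, regional and distant categories in 7.2(c) suggest that site will be known, but the plan does not say so.

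A third is that nothing turns on it. The endpoint is secondary, the sample size and review rule rest on cosmesis, and the likely difference is an event or two in 40. This stands too, and it limits the severity.

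A reader might infer more than the documents support, in three ways:

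- *That the comparison is biased against the new technique.* No historical series or endpoint is named, and against a locoregional benchmark this bias disappears.
- *That the composite doubles the failure rate.* At L = 5% that needs a regional risk close to 5%, the top of the assumed range (9.75/5 = 1.95). No difference at all is also possible.
- *That censoring deaths is an error.* It is pre-specified, its effect is small, and replacing it could create a mismatch with a Kaplan-Meier benchmark.

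**Conclusion.** The mismatch is confirmed from the text alone: objective 3 is in-breast control, and no in-breast estimate is planned. This does not depend on any assumed rate.

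The size does depend on assumptions. With 5% local risk, 0% to 5% regional risk and independence, the composite exceeds local failure by 0 to about 5 points, which is well inside the sampling uncertainty of 40 patients. Whether it would make the technique look worse than history is conditional on an in-breast benchmark. The objective's wording suggests one, but the documents do not identify it.

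Severity is minor to moderate: a secondary objective and its analysis disagree, the repair is cheap, and no decision rule uses the endpoint.

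**What to change.** In Section 7.2(c):

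1. Add time to local failure, from start of treatment to first recurrence in the treated breast. State that regional and distant failures neither count as events nor end follow-up for it.
2. Define the analysis set as the breast-conservation subjects, with those who need mastectomy reported separately, consistent with Section 5.2.
3. Report the estimate with its 95% CI at one stated follow-up year, beside a named historical rate that uses the same endpoint and the same estimator. Describe the comparison as descriptive only.
4. Keep the local-or-regional and distant failure curves as supportive.
5. Optionally, add cumulative incidence with death as a competing event as a sensitivity analysis.

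Confirm that the case report form records site of failure, and that breast recurrence is still recorded after a regional failure. If so, the cost is one definition and one extra curve, with no additional patients or visits.

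### Section 7.2(c) should report cumulative incidence with death as a competing event beside the death-censored Kaplan-Meier curves; the expected difference is small

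*Combined protocol and SAP*

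**What the plan says.** Section 7.2(c) sets up two failure-time endpoints, both measured from the start of treatment. For local or regional failure, "distant failures will be ignored; deaths will be censored". For distant failure, "local and regional failures will be ignored; deaths will be censored". The estimator is the same for both: "The Kaplan Meier method will be used to estimate both of these distributions". No cumulative incidence function, competing-risk method or sensitivity analysis appears anywhere in the document. Unlike 7.2(a) and (b), item (c) mentions no confidence interval.

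The local endpoint serves secondary objective 3 in Section 3.1: "Assess local control in the treated breast relative to historical controls". The historical series is not identified, and neither its failure rate nor its estimator is given.

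On duration, Section 6.3 describes visits "every 6 months to a year through year 5 and annually through year 10", and the Section 6 footnote recommends them "every 6 months through year 5 and annually years 5-10". Section 6.3 adds: "Locoregional recurrence will be monitored on protocol at each follow-up visit". Section 7.2(c) fixes no time at which either curve is to be read.

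**The concern.** A woman who dies can no longer have a local, regional or distant failure. Censoring her at death lets the Kaplan-Meier curve proceed as if she could still fail, at the rate of the women who remain. 1-KM then describes failure in a setting without death, and it does so only if death is independent of failure risk. It is not the proportion of treated women who fail, which is how most readers will take a local control figure.

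The independence assumption is weakest for the local endpoint. Because distant failures are ignored there, a woman with metastatic disease stays in the risk set until she dies and is then censored. Her risk of local failure may well differ from that of the women still followed. The documents do not discuss this.

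At stake is the meaning of the one failure figure that is to be set against historical controls. If the historical figure is a true proportion failing and the trial figure is 1-KM, the two sides measure different things.

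**Working it through.** **Figures in the plan.** The document states no figure for these endpoints, so there is none to reproduce. The only decision rule, on 6-month cosmesis in Section 7.1, was recomputed to see whether it is touched. The exact probability of a review (8 or more fair/poor of 20, or 12 or more of 40) is 0.9326 at a true good/excellent rate of 0.60 and 0.0983 at 0.80. The plan states 0.93 and 0.10. Both agree, and neither uses a failure time.

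**Direction.** At each failure time, Kaplan-Meier adds S_KM × d/n to the failure estimate, and Aalen-Johansen adds S_all × d/n. Here d is the number failing, n the number at risk, S_KM the failure-free curve with deaths censored, and S_all the curve free of both failure and death. S_all is never above S_KM, so 1-KM is never below the cumulative incidence (CIF). Example with 40 women fully followed: if one dies and another then fails, 1-KM = 1/39 = 2.56% and CIF = 1/40 = 2.50%. If the failure comes before the death, both are 1/40.

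**Size.** Inputs from the document: 40 women, single arm (Section 7.1). Inputs assumed, because none are given: constant hazards h1 (failure) and h2 (death without failure), set so that each cause acting alone would reach F and D by year 10:

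- h1 = -ln(1-F)/10 and h2 = -ln(1-D)/10
- 1-KM(t) = 1 - exp(-h1·t)
- CIF(t) = h1/(h1+h2) × [1 - exp(-(h1+h2)·t)]
- CI half-width ≈ 1.96 × √(p(1-p)/40), with p = 1-KM

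Worked case, F = 10% and D = 20%: h1 = 0.01054 and h2 = 0.02231. CIF(10) = 0.01054/0.03285 × (1 - 0.90 × 0.80) = 0.3207 × 0.28 = 8.98%, against 1-KM = 10.00%.

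| F at 10 y | D at 10 y | 1-KM | CIF | Excess (points) | CI half-width (points) |
|---|---|---|---|---|---|
| 5% | 5% | 5.00% | 4.88% | 0.13 | 6.8 |
| 5% | 10% | 5.00% | 4.75% | 0.25 | 6.8 |
| 5% | 20% | 5.00% | 4.49% | 0.51 | 6.8 |
| 10% | 5% | 10.00% | 9.75% | 0.25 | 9.3 |
| 10% | 10% | 10.00% | 9.50% | 0.50 | 9.3 |
| 10% | 20% | 10.00% | 8.98% | 1.02 | 9.3 |
| 20% (extreme) | 30% | 20.00% | 16.93% | 3.07 | 12.4 |

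**Earlier times.** With F = 10% and D = 5%, 10% or 20%, the excess is 0.02, 0.05 or 0.10 points at 3 years and 0.06, 0.13 or 0.27 points at 5 years.

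**Simulation.** 20,000 trials of 40 women with complete 10-year follow-up gave:

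| F / D | Mean excess (points) | Trials with no difference | SD of 1-KM (points) |
|---|---|---|---|
| 5% / 5% | 0.13 | 41% | 3.5 |
| 10% / 10% | 0.50 | 10% | 4.9 |
| 10% / 20% | 1.02 | 4% | 5.1 |

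The half-widths are a yardstick only. With 2 to 4 expected failures (40 × 4.88% = 1.95; 40 × 9.50% = 3.80) the normal approximation is crude. Section 5.2 also records women who need mastectomy separately, so the number analysed may be below 40.

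**The case against.** The strongest defence is that 7.2(c) never claims to estimate the proportion failing. It says that Kaplan-Meier will estimate the distributions of two failure times, and the death-censored curve is a recognised estimate of the net distribution when deaths are independent of failure risk. This stands: the gap is that the quantity wanted is not named, and the bias arises only if 1-KM is read as a proportion. The independence that the net reading needs is neither stated nor defended, so the defence does not remove the need for a change.

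A reader might also infer that the plan overstates failure by 1 to 2.5 points over ten years of follow-up. The documents do not support that. They schedule visits to year 10, partly as recommended or guideline care, but plan no 10-year estimate. They give no death rate either. An excess of that order needs something like failure at 1% or 2% a year with death at 2% or 3% a year (9.5% against 8.6%, and 18.1% against 15.7%). Those death hazards mean about 18% (1 - e^-0.2) and 26% (1 - e^-0.3) dead by year 10, and Section 3.4 describes typical candidates with invasive cancer as under 60. Older women and T3 tumours are allowed, so such rates cannot be excluded, but they are not the natural central case.

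A third inference would be that the technique will look worse than history. That follows only if the historical rate is a cumulative incidence. If it came from death-censored Kaplan-Meier, the present plan is like for like, and replacing Kaplan-Meier outright would tilt the comparison in favour of the technique.

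Finally, no objective in Section 3.1 mentions distant failure, so for that endpoint the point concerns description only.

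**Conclusion.** The point holds as a cheap improvement, not as an error that threatens a conclusion. Read as the proportion failing, death-censored 1-KM can only err upward, and the independence that would justify a net reading is doubtful for the local endpoint. Over the 5-10% failure and 5-20% death range, the excess at 10 years is at most about one ninth of the CI half-width (1.02/9.3 = 0.11). All sizes rest on assumed constant, independent hazards and complete follow-up. They therefore do not measure any effect of dependence between death and local failure, which the documents give no means to quantify. No test, power calculation, threshold or stopping rule is affected.

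**What to change.** In Section 7.2(c):

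- Name the quantity and the time or times at which it will be read.
- Report the Aalen-Johansen cumulative incidence of each endpoint, with death without that event as a competing event and 95% CIs, as the estimate of the proportion failing. This does not need death to be independent of failure risk.
- Keep the Kaplan-Meier curve beside it, labelled as censoring deaths.
- For objective 3, name the historical series and compare using the estimator that series used.

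The cost is one extra standard analysis, a few sentences in 7.2(c), and two curves to explain instead of one. Dates of death are already needed for the planned censoring, so no new data are required, and the sample size is unchanged.
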